## **5.12 Analysis of Secondary Endpoint**

Mean Profile 29+2 scores for each arm at day 120 will be compared using a two-sample *t*-test (or Wilcoxon Rank Sum test if non-normality is apparent) with a significance level of 0.05. Linear regression models will be performed to

complement the results of the *t*-test and adjust for specific baseline caregiver characteristics (e.g., demographic, social, environmental) to increase the precision of our inference. There is a possibility that patient characteristics will be unbalanced since our randomization scheme will be applied to caregivers. Thus, our models also will assess potential moderating or mediating effects, described below.

## **5.13 Analysis of Exploratory Endpoints**

### **5.13.1 Caregiver and patient demographics and baseline characteristics**

Caregivers in each arm (treatment vs. control) will be compared descriptively according to Consolidated Standards of Reporting Trials Guidelines. Continuous measures will be described using means and standard deviations (or medians and ranges if non-normality is apparent), while categorical measures will be summarized with frequencies and percentages. Formal comparisons will be made between the arms, although no significant differences are expected due to the randomization of the arm assignments. Similar summaries will be done for patient characteristics.

### **5.13.2 Caregiver and patient PROs (see Appendix C)**

All questionnaires will be scored according to coding manuals. The resulting scores will be compared between arms at baseline and days 30 and 120 using the Wilcoxon Rank Sum test. Outcome measures will be compared between arms using linear regression modeling of day 30 and day 120 outcomes after adjusting for baseline scores. We also will model the outcomes from all three time points simultaneously using a linear mixed model to account for within-subject correlation, as well as adjust for possible moderating or mediating characteristics of the caregiver or patient.

### **5.13.3 Caregiver and patient overall survival**

Death from any cause will be calculated from randomization to death or loss to follow-up. Participants alive at last follow-up will be censored. Survival curves will be calculated for each arm using the methods of Kaplan and Meier and will be compared between arms using the log-rank test.

### **5.13.4 Mediation and moderation**

Our assessment for potential mediation will follow the Baron and Kenny approach. Specifically, we will first fit models examining the effect of the intervention on our dependent variables. We will refer to the treatment effect estimates from these models as Estimates A. We will then fit each of our models again, but with all potential mediators included as covariates. We will refer to the parameter estimates for these covariates as Estimates B. We will then apply the Baron and Kenny

approach to Estimates A and B to determine the direct and indirect effects of the intervention on each of the dependent variables, with corresponding standard error estimates determined using bootstrap methods, as described by Whittle, et al. These models will be adjusted for any confounders that are discovered, although we expect the randomization to account for most confounding. Moderation will be assessed by including main effects of potential moderators and interaction terms of each potential moderator with the intervention.

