#### 5.13.6 Caregiver and patient health care utilization

The total count of hospital days, ED visits, readmissions, and ambulatory care clinic visits within the first 120 days post-BMT, with adjustment for follow-up, will be compared between arms using a Poisson regression model, with adjustment for potential mediating or moderating effects of patient or caregiver characteristics, if needed. The data will be captured at the time of PRO assessments. Subjects will remain in follow-up for 1-year post-HCT. The study team will have access to the electronic medical record for 1-year post-HCT.

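### The estimates defined in 5.13.4 cannot give mediator-specific effects, and two exploratory arm comparisons may adjust for variables the intervention has changed

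*Combined protocol and SAP*

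**What the plan says.** Section 5.13.4 names its method: "Our assessment for potential mediation will follow the Baron and Kenny approach". It then sets out the steps.

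- Models of each dependent variable on the intervention are fitted first. "We will refer to the treatment effect estimates from these models as Estimates A".
- The models are then extended: "We will then fit each of our models again, but with all potential mediators included as covariates". The mediator terms get their own label: "We will refer to the parameter estimates for these covariates as Estimates B".
- Direct and indirect effects come from a Baron and Kenny mediation "approach to Estimates A and B to determine the direct and indirect effects of the intervention on each of the dependent variables"; standard errors are to be bootstrapped.

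The section gives no regression of a mediator on arm, and the statistical section names no mediators.

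Two other exploratory analyses use mediators as covariates. In 5.13.2, the mixed model over all three time points will "adjust for possible moderating or mediating characteristics of the caregiver or patient". In 5.13.6, the Poisson model for utilization compares arms "with adjustment for potential mediating or moderating effects of patient or caregiver characteristics", where this is judged necessary.

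The other comparisons are cleaner. Sections 5.11 and 5.12 test arms with an unadjusted t-test or Wilcoxon test, supplemented by regressions on baseline caregiver characteristics. They say only that mediation will be assessed as described later. Section 5.13.2 also plans a Wilcoxon comparison and a regression of day-30 and day-120 scores adjusted for the baseline score alone.

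**The concern.** A mediation analysis needs three quantities besides the total effect: the effect of arm on the mediator, the effect of the mediator on the outcome given arm, and the effect of arm on the outcome given the mediator. The labelled inputs in 5.13.4 supply only the second. The third is fitted when the models are rerun, because the arm term stays in, but it is not designated for use. The first is not linked to the calculation at all.

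This matters because the protocol has a mechanism aim. Section 1.2 lists poor understanding of mechanism among the barriers to translating caregiver interventions, and 1.6 hopes that sensor and PRO data together will help to identify it. Saying which mediator carries an effect requires mediator-specific indirect effects.

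The second issue is separate. An arm comparison adjusted for something the intervention has changed no longer estimates the difference between arms. It estimates what remains when that pathway is held fixed. Reported beside the other PRO and utilization comparisons, it could be mistaken for the treatment effect.

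**Working it through.** **The plan's own figure.** Section 5.13.4 gives no number. The only power statement is in 5.7: 67 caregivers per arm, 0.5 SD (5 points on an SD of 10), two-sided 0.05, power 0.80. It serves here only to scale an illustration. The exact t-test needs 63.77, so 64 per arm. Dividing by the Wilcoxon efficiency 3/π gives 66.78, so 67 per arm with power 0.801. The t-test at 67 per arm has power 0.819. The figure reproduces.

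**Notation.** Let c be the arm effect on the outcome without mediators (Estimates A), b the mediator coefficient with arm in the model (Estimates B), c′ the arm coefficient in that same model, and a the effect of arm on the mediator. For least-squares models fitted to the same participants, c = c′ + a×b, so the indirect effect is a×b = c − c′.

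**Do A and B determine the answer?** Hold c = 5 and b = 0.5, and vary a. Illustrative assumptions: outcome and mediator SD 10, one mediator, no unmeasured common cause of mediator and outcome. Results are averages over 4,000 simulated trials of 67 per arm.

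| a | True indirect, a×b | True direct, 5 − a×b | Simulated c′ | Simulated a×b | Simulated c − c′ | Chance of significance, unadjusted | Chance of significance, adjusted for mediator |
|---|---|---|---|---|---|---|---|
| 0 | 0 | 5.00 | 4.98 | 0.01 | 0.01 | 0.82 | 0.91 |
| 2.5 | 1.25 | 3.75 | 3.72 | 1.26 | 1.26 | 0.82 | 0.69 |
| 5 | 2.50 | 2.50 | 2.51 | 2.50 | 2.50 | 0.82 | 0.37 |
| 10 | 5.00 | 0 | 0.02 | 4.95 | 4.95 | 0.82 | 0.05 |

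Every row has the same A and B up to simulation error, yet the indirect effect runs from none of the total to all of it. Adding either c′ or a resolves the single-mediator linear case.

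**Several mediators.** The plan enters all potential mediators together. Take two, each with b = 0.5, and c′ = 2.5. Arm effects on the pair of (5, 0), (0, 5) or (2.5, 2.5) all give c = 2.5 + 0.5×5 = 5 and c − c′ = 2.5. The mediator-specific effects are 2.5/0, 0/2.5 and 1.25/1.25. Thus A, B and c′ can all agree while the mechanism differs; only the a paths separate the cases.

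**Non-linear outcomes.** The identity c − c′ = a×b belongs to linear models. It does not carry over in general to the Poisson model in 5.13.6.

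**Adjusting the arm comparison.** If the total is 5, arm raises the mediator by 4, and the mediator coefficient is 0.4, the indirect effect is 4×0.4 = 1.6. The adjusted arm coefficient is 5 − 1.6 = 3.4, which is 32% below the total (1.6/5). If the indirect effect were −1.6, the adjusted coefficient would be 5 + 1.6 = 6.6. The last two columns of the table show the effect on the chance of a significant arm term.

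**The case against.** The other side has four good arguments.

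**The missing pieces are largely present elsewhere.** The named method conventionally includes an arm-to-mediator step. The regression in 5.13.2 of day-30 scores on arm and baseline is already that model for any PRO mediator, and 5.13.5 compares sleep variables between arms. This stands, and it makes the remedy cheap. But 5.13.4 spells out its own steps and draws on neither section, so an analyst following the text would not use those models.

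**The direct effect is fitted.** This also stands. A reader might infer that the indirect effects would simply be wrong. The documents do not support that, because c − c′ gives a valid joint indirect effect for linear outcomes under the usual assumptions.

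**No formula is stated.** A reader might infer that Estimates A and B would be multiplied together, and compute an error from that. The plan never states that product, so no bias figure can be attached to it.

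**The adjustment variables may be baseline traits.** Sections 5.13.2 and 5.13.6 refer to caregiver or patient characteristics, and 5.11 raises mediation in connection with chance imbalance in patient characteristics. On that reading the estimate stays at about 5 and the chance of significance rises to 0.91 (first row of the table). This stands as a condition. However, a variable fixed before randomization cannot mediate the intervention's effect, and 5.11 and 5.12 say baseline where they mean it.

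Two further inferences fail. Adjusted effects need not shrink toward zero, because the direction follows the sign of the indirect effect. The primary result is not at risk either, because its test and its supporting regression include no stated mediator adjustment.

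**Conclusion.** The concern holds as an incomplete specification in 5.13.4 and a conditional change of estimand in 5.13.2 and 5.13.6. The first part rests only on how the plan defines its two sets of estimates. The second depends on the covariates being measured after the intervention begins and being changed by it. The sizes shown are illustrations under assumed coefficients, not predictions for this trial.

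The scope is limited. The primary and secondary tests are unaffected, and 5.13.2 reports a PRO comparison adjusted for baseline score only in any case. The exposed items are the mediation analysis (including its application to the primary outcome), the PRO mixed model, and the utilization model if the optional adjustment is made. The text should be corrected before analysis, but the point does not threaten the trial's main conclusion.

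**What to change.** **In 5.13.4**

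- Name the candidate mediators and when each is measured. Day-30 mediators suit day-120 outcomes: under 4.8 the windows are 30 ± 14 and 120 ± 30 days, so the latest mediator (day 44) precedes the earliest outcome (day 90).
- For each mediator, regress it on arm and its own baseline, using the 5.13.2 model where that already exists.
- Define the direct effect as the arm coefficient in the outcome model containing all mediators.
- For linear outcomes, define each indirect effect as the arm-to-mediator coefficient times that mediator's coefficient in the joint model, with bootstrap confidence intervals.
- For Poisson outcomes, use a causal mediation estimator suited to non-linear models, not the simple product.

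**In 5.13.2 and 5.13.6**

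- Remove mediating variables from the adjustment, and restrict covariates in arm comparisons to baseline, pre-intervention variables that assignment cannot have changed. Requiring measurement before randomization would be too strict: 4.6 collects caregiver data within 30 days of randomization, and 4.7 requires baseline PROs only to precede the intervention.

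The cost is SAP wording and at most one extra regression per mediator. No new data are needed. The Poisson case takes somewhat more programming than a product of coefficients.

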## 1.6 Biomarkers Relevant to Caregiving Efforts

Caregivers experience significant stress, anxiety, and poor sleep that lead to physiological changes. Indeed, long-term caregiving has been associated with increased physical morbidity. While caregiver interventions have been shown to reduce emotional distress and increase well-being in caregivers, less is known about the impact of physiological changes on caregiver health and well-being. Caregiver assessments have relied on snapshot self-report measures (i.e., patient-reported outcomes [PROs]). Recent advances in wearable sensors facilitate non-invasive collection of continuous, real-time measures (e.g., sleep, physical activity). These highly time-resolved, *objective* parameters correlated with *subjective* PROs may help us identify the mechanism of action of an intervention. Further, newer data science techniques may enable data patterns, relationships, and interpretation in ways that were not previously possible.

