#### **3.2 Exploratory Endpoints**

- 3.2.1 Caregiver HRQOL will be assessed by the PROMIS Global Health and Profile 29+2 scales at baseline (pre-intervention) and days 30 post-HCT.
- 3.2.2 Caregiver and patient HRQOL will be assessed by the PROMIS Companionship scale at baseline (pre-intervention), and days 30 and 120 post-HCT.
- 3.2.3 Caregiver and patient HRQOL will be assessed by the PROMIS Self-Efficacy for Managing Symptoms and Self-Efficacy for Managing Daily Activities scales at baseline (pre-intervention), and days 30 and 120 post-HCT.
- 3.2.4 Caregiver and patient HRQOL will be assessed by the PROMIS Positive Affect and Well-Being scale at baseline (pre-intervention), and days 30 and 120 post-HCT.
- 3.2.5 Caregiver and patient HRQOL will be assessed by the PROMIS Emotional Support at baseline (pre-intervention), and days 30 and 120 post-HCT.

- 3.2.6 Caregiver and patient HRQOL will be assessed by the Perceived Stress Scale at baseline (pre-intervention), and days 30 and 120 post-HCT.
- 3.2.7 Caregiver and patient HRQOL will be assessed by the Resilience, Optimism and Gratitude scales at baseline (pre-intervention), and days 30 and day 120 post-HCT.
- 3.2.8 Patient HRQOL will be assessed by the PROMIS Sleep Disturbance scale at baseline (pre-intervention), and days 30 and 120 post-HCT.
- 3.2.9 Caregiver and patient negative and positive dyadic interaction will be assessed by measures of the Dyadic Relationship Scale at baseline (pre-intervention), and days 30 and 120 post-HCT.
- 3.2.10 Caregiver HRQOL will be assessed by the TBI-CareQOL (PROMIS affiliate) Caregiver Anxiety at baseline (pre-intervention), and days 30 and 120 post-HCT.
- 3.2.11 Caregiver HRQOL will be assessed by the TBI-CareQOL (PROMIS affiliate) Caregiver Strain scale.
- 3.2.12 Activity data. Caregiver and patient activity (steps) and sleep will be measured continuously from the start to the end of the intervention (day 120 post-HCT) through wearable sensors.

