## **5.0 STATISTICAL CONSIDERATIONS**

### **5.1 Study Design**

This study will use a two-arm randomized design. Each caregiver-patient dyad will be randomized to an active “treatment” arm (mobile platform + Roadmap 2.0) or to a control arm (Mobile platform + usual care). The random allocation of participants to the treatment arm or control arm establishes the basis for testing the statistical significance or difference between the groups in the measured outcome (caregiver health-related quality of life, assessed by the PROMIS Global Health scale). Caregiver age, gender, and other prognostic baseline characteristics that could potentially confound an observed association, including those that are unknown or unmeasured, will be distributed equally, except through chance alone, through random assignment. Thus, this design is well-suited to our goal of assessing the efficacy of a mobile health intervention, Roadmap 2.0, on caregivers.

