## **5.11 Analysis of Primary Endpoint**

Analysis will be an intent-to-treat analysis that includes all caregivers. Mean Global Health scores for each arm at day 120 will be compared using a two-sample *t*-test (or Wilcoxon Rank Sum test if non-normality is apparent) with a significance level of 0.05. Linear regression models will be performed to complement the results of the *t*-test and adjust for specific baseline caregiver characteristics (e.g., demographic, social, environmental) to increase the precision of our inference. We plan to do analyses separately for allo dyads, auto dyads, and pediatric dyads, although we have only powered the study for the analysis in the allo dyads. There is a possibility that patient characteristics will be unbalanced since our randomization scheme will be applied to caregivers. Thus, our models also will assess potential moderating or mediating effects, described below.

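### Randomizing the arm does not protect the mediator-to-outcome path, so the indirect and direct effects in 5.13.4 could be biased in either direction

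*Combined protocol and SAP*

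**What the plan says.** Section 5.13.4 follows the Baron and Kenny approach. The arm effect on each dependent variable is estimated first. Then: "We will then fit each of our models again, but with all potential mediators included as covariates". Direct and indirect effects are derived from the two sets of estimates, "with corresponding standard error estimates determined using bootstrap methods". On confounding the section has one sentence: "These models will be adjusted for any confounders that are discovered, although we expect the randomization to account for most confounding".

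What is randomized is the arm of the dyad (5.1): "Each caregiver-patient dyad will be randomized to an active “treatment” arm". Mediator values are observed afterwards.

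The mediation plan sits under exploratory endpoints, but 5.11 points to it for the primary-endpoint models ("Thus, our models also will assess potential moderating or mediating effects, described below"), and 5.12 does the same for the Profile 29+2 models.

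Baseline adjustment appears in two other places. Section 5.13.2 says of the PRO regressions: "Outcome measures will be compared between arms using linear regression modeling of day 30 and day 120 outcomes after adjusting for baseline scores". Section 5.11 adjusts its complementary regressions for baseline caregiver characteristics and gives demographic, social and environmental ones as examples; it does not name baseline Global Health.

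Section 5.13.4 names no mediators, no confounders fixed in advance, no adjustment for the baseline mediator, no time order and no sensitivity analysis for residual confounding. The data for most of these exist: section 3.2 collects caregiver PROs repeatedly, for example the "PROMIS Positive Affect and Well-Being scale at baseline (pre-intervention), and days 30 and 120 post-HCT".

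**The concern.** An indirect effect combines two links: how far the arm shifts the mediator, and how the mediator relates to the outcome within arms. Randomization makes the first link, and the total effect, comparable between arms. It does nothing for the second. A caregiver with better baseline mood, health or support is likely to score higher on, say, self-efficacy and on Global Health in either arm. Such a trait can be perfectly balanced between arms and still create a mediator-outcome association that is not causal. The expectation in 5.13.4 is therefore wrong for the path that separates an indirect from a direct effect. Bootstrap standard errors describe sampling error and leave this bias in place.

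At stake is the interpretation of how the intervention works. Section 1.6 says that sensor data correlated with PROs "may help us identify the mechanism of action of an intervention". Candidate mediators suggested by the background, such as self-efficacy (1.4, 1.5), are reported by the same caregiver who reports the outcome, so shared causes are plausible.

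**Working it through.** **The plan's own figure.** The documents give no figure for mediation, so the sample size in 5.7 only sets the scale. For 0.5 SD, two-sided 0.05 and power 0.80, a t-test needs 64 per arm. Dividing the unrounded 63.77 by 3/π (0.955) for a Wilcoxon test gives 66.8, so the stated 67 reproduces. With 83 per arm and the losses in 5.7, 83 × 0.95 × 0.92 × 0.90 = 65.3, hence 65 evaluable per arm below.

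**Assumptions, not in the documents.** One baseline trait C, independent of arm T, has correlation r with mediator M and outcome Y within arms. The arm moves M by a. M has no effect on Y, so the true indirect effect is zero. M and Y have within-arm SD 1.

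**Formula.** If C is omitted, the coefficient of M in the outcome model is cov(M,Y|T)/var(M|T) = r². The spurious indirect effect is therefore a × r², and the direct effect is off by the same amount with the opposite sign, because the total is unbiased. If the trait raises M and lowers Y, the bias is −a × r² and could hide a real indirect effect.

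**Results without adjustment, 65 per arm.** Percentages are simulated trials whose 95% bootstrap interval excludes zero; ranges are over repeat runs.

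| r | a = 0.5: a × r² | a = 0.5: excludes zero | a = 0.2: a × r² | a = 0.2: excludes zero |
|---|---|---|---|---|
| 0.3 | 0.045 SD | 14–17% | 0.018 SD | about 4% |
| 0.5 | 0.125 SD | 65–73% | 0.050 SD | about 20% |
| 0.6 | 0.180 SD | 80–83% | 0.072 SD | about 22% |

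Simulated means at a = 0.5 were about 0.04–0.05, 0.13 and 0.18–0.19 SD, in line with the formula. Against a total effect of 0.5 SD these are 0.045/0.5 = 9%, 25% and 36% apparently mediated. At a = 0 the formula gives zero bias, and intervals excluded zero in 2–8% of trials. With C in both models at a = 0.5, the indirect effect was about 0 and 5–7% of intervals excluded zero.

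**Sample size does not cure it.** With a = 0.5 and a within-arm mediator-outcome correlation of 0.3 due only to the shared cause (r = √0.3 = 0.55), the expected bias is 0.5 × 0.3 = 0.15 SD, or 1.5 T-score points at SD 10. Simulation gave 0.153 SD and 80% at 67 per arm. At 130 per arm (all 260 adult dyads, no loss) it gave 0.148 SD and 98%.

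**Imperfect adjustment helps only in part.** In that scenario at 67 per arm, suppose the adjusted proxy carries a share q of the trait's variance. The bias is then 0.5 × 0.3(1 − q)/(1 − 0.3q).

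| q | Formula | Simulated | Excludes zero |
|---|---|---|---|
| 0.25 | 0.122 SD | 0.121 SD | 67% |
| 0.50 | 0.088 SD | 0.087 SD | 45% |
| 0.75 | 0.048 SD | 0.048 SD | 19% |
| 1.00 | 0 | 0.000 SD | 7% |

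**The case against.** The strongest reply is that the plan already does some of this. Section 5.13.4 refits the existing models, and on a natural reading the refitted PRO regressions of 5.13.2 keep the baseline outcome score. In the scenario above, having the trait in the outcome model alone is enough: the indirect effect falls to near zero and 4–7% of intervals exclude it. This stands, so a reader should not infer that the plan has no baseline adjustment. It does not close the gap: a baseline outcome score is an imperfect stand-in for all shared causes, the baseline mediator is not required, and 5.11 does not name baseline Global Health.

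A reader might also infer that only confounders unbalanced between arms would count as discovered, so that balanced traits are never adjusted for. Section 5.13.4 does not say so; a confounder can be found through its association with mediator and outcome. The term is undefined, however. If it were applied as adjusting only when arms differ at p < 0.05, a simulation at 65 per arm and a = 0.5 still gave 0.120 SD and 64% at r = 0.5, against 0.128 SD and 67% with no adjustment.

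Finally, mechanism is not a listed objective. The sentence in 1.6 is background about wearable data, and no objective in the synopsis or 2.3 mentions mediation. That limits the weight of the point.

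**Conclusion.** The point holds in a conditional form. The expectation about randomization is wrong for the mediator-to-outcome path, and indirect and direct effects could be biased in either direction.

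A reader might go further and conclude that false indirect effects would be reported. The documents do not support that. Such a result needs both an arm effect on the mediator and an unadjusted shared cause, and the plan does promise some adjustment. With no adjustment at all, the illustration runs from no bias (a = 0), through 0.02–0.07 SD and 4–22% of intervals excluding zero (a = 0.2 SD), to 0.05–0.18 SD and 14–83% (a = 0.5 SD). The correlations, the mediator shifts and the single shared trait are assumptions; the documents give none of them. The actual bias under the plan would be smaller to the extent that the baseline outcome score and other adjusted covariates capture the shared causes.

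The primary between-arm comparison does not use the mediator and is unaffected. The analysis is exploratory, but it is worth correcting because the correction uses data already planned.

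**What to change.** Replace the confounding sentence in 5.13.4 with:

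> Randomization does not remove confounding between mediator and outcome. Each mediator model and each outcome model will include, regardless of balance between arms, the baseline score of the outcome and, where collected, of the mediator, plus a short prespecified list of baseline common causes.

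Writing that list means naming the candidate mediators first. It should stay short. Forcing in all nine caregiver characteristics of 5.9 would cost more degrees of freedom, and none of them is baseline mood or emotional support. The words *where collected* matter because 3.2.12 describes activity and sleep as measured from the start of the intervention.

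Where a day 30 mediator is available, pair it with the day 120 outcome. The windows in 4.8 keep the order: the latest day 30 assessment is day 44 (30 + 14) and the earliest day 120 assessment is day 90 (120 − 30). The drawback is that mediator changes after day 30 are missed although the intervention runs to day 120.

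Add a sensitivity analysis showing how strong residual mediator-outcome confounding would have to be to remove each reported indirect effect, since imperfectly measured causes are only partly adjusted away.

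The cost is SAP wording, a few degrees of freedom and some extra analysis. Baseline outcome measures are already a condition of the analysis population (5.10.1), and the PROs need no new data collection.
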